7.4.2 Obinutuzumab Dose Modifications

Dosage modifications during treatment (all indications)

No dose reductions of obinutuzumab are recommended. Dose delays should be considered in case of severe or life-threatening neutropenia or thrombocytopenia. For management of symptomatic adverse events (including IRRs), please refer to Table 5 below

Table 5: Infusion rate modification guidelines for infusion related reactions (IRRs)

Grade 4 (life threatening)	Stop infusion and discontinue therapy.
Grade 3 (severe)	Temporarily interrupt infusion and treat symptoms. Upon resolution of symptoms, restart infusion at no more than half the previous rate (the rate being used at the time that the IRR occurred) and, if participant does not experience any IRR symptoms, infusion rate escalation may resume at the increments and intervals as appropriate for the treatment dose (Section 7.1.2). For CLL patients receiving the Cycle 1, Day 1 dose split over 2 days, the Day 1 infusion rate may be increased back up to 25 mg/hr after 1 hour, but not increased further. If the patient experiences a second occurrence of a Grade 3 IRR, stop infusion and permanently discontinue therapy.
Grade 1-2 (mild and moderate)	Reduce infusion rate and treat symptoms. Upon resolution of symptoms, continue infusion and, if participant does not experience any IRR symptoms, infusion rate escalation may resume at the increments and intervals as appropriate for the treatment dose (Section 10.5).

	For CLL patients receiving the Cycle 1, Day 1 dose split over 2 days, the Day 1 infusion rate may be increased back up to 25 mg/hr after 1 hour, but not increased further.
--	---

Patients should not receive further obinutuzumab infusions if they experience:

- acute life-threatening respiratory symptoms,
- a Grade 4 (i.e., life-threatening) IRR or,
- a second occurrence of a Grade 3 (prolonged/recurrent) IRR (after resuming the first infusion or during a subsequent infusion)

7.4.3 Management of obinutuzumab delays

Treatment with obinutuzumab may be discontinued due to poor tolerability/toxicity at the discretion of the treating physician. For patients with evidence of TLS, drug should be discontinued and the patient treated as clinically indicated. Following complete resolution of TLS complications, the study drug may be re-administered at the full dose during the next infusion in conjunction with prophylactic therapy.

a) Haematological Toxicity

Thrombocytopenia: Special Considerations

- Patients treated with concomitant medication which could possibly worsen thrombocytopenia related events may be at greater risk of bleeding. Patients should be closely monitored for thrombocytopenia, especially during the first cycle; regular laboratory tests should be performed until the event resolves, and dose delays should be considered in case of severe or life-threatening thrombocytopenia.
- Participants who experience G3/4 thrombocytopenia ($<25.0 -50 \times 10^9 /L$) should be closely monitored and transfusion of blood products at the discretion of the treating clinician.

Neutropenia

- For participants who experience G3/4 neutropenia ($<0.5 -1.0 \times 10^9 /L$), we recommend treatment with G-CSF and to delay obinutuzumab until the neutrophils are back above $0.5 \times 10^9 /L$

b) Non-Haematological Toxicity

- If hypersensitivity to obinutuzumab occurs (typically occurring after previous exposure to obinutuzumab), the infusion should be stopped and treatment permanently discontinued. Participants with a known IgE mediated hypersensitivity to obinutuzumab should not be treated.
- Obinutuzumab should not be administered in the presence of a severe infection.
- Prophylactic therapy aimed at preventing a recurrence of a diagnosed infection should be instituted if clinically indicated.

c) Progressive multifocal leukoencephalopathy (PML)

- Cases of PML have been reported in patients treated with anti-CD20 antibodies including obinutuzumab.
- Treatment with obinutuzumab should be withheld during the investigation of potential PML and permanently discontinued in the event of a confirmed diagnosis.

d) Infusion Related Reactions

- If a participant develops hypotension during obinutuzumab IV infusions, the withholding of antihypertensive treatments should be considered at the discretion of the treating clinician for

12 hours prior to and throughout obinutuzumab infusions and for the first hour after administration.

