7.4.1 Ibrutinib

Recommendations for Ibrutinib dose modifications are provided in Table 4; variations from these recommendations may be warranted based on an investigator's individual judgment in considering potential risks, benefits, and therapeutic alternatives available to each subject.

The ibrutinib dose should be withheld for any unmanageable, potentially drug-related toxicity that is Grade 3 or higher in severity. Any other clinically important events where dose delays may be considered appropriate by the Investigator must be discussed with the clinical coordinator via the trials office.

Ibrutinib may be withheld for a maximum of 28 consecutive days for toxicity. Study treatment should be discontinued in the event of a toxicity lasting more than 28 days.

The dose of ibrutinib should be modified according to the dose modification guidelines in Table 4 if any of the following toxicities occur:

- Grade 4 neutropenia ($0.5 \times 10^9/L$) for more than 7 days. The use of neutrophil growth factors is permitted.
- Grade 3 thrombocytopenia ($50 \times 10^9/L$) for subjects with normal platelet count at baseline; or, for subjects with baseline thrombocytopenia, a platelet decrease of 50% to 74% from baseline in the presence of significant bleeding.
- Grade 4 thrombocytopenia ($25 \times 10^9/L$); or for subjects with baseline thrombocytopenia, a platelet decrease of $\geq 75\%$ from baseline or $< 20 \times 10^9/L$, whichever is higher.
- Grade 3 or 4 nausea, vomiting, or diarrhoea if persistent, despite optimal anti-emetic and/or anti-diarrheal therapy.
- Any other Grade 4 toxicity
- Any unmanageable Grade 3 toxicity

Table 4: Recommendations for ibrutinib dose modifications

Events	Occurrence	Action to be Taken
Grade 2 cardiac failure	First	Withhold until recovery to \leq Grade 1 or baseline; may restart at 280 mg daily
	Second	Withhold until recovery to \leq Grade 1 or baseline; may restart at 140 mg daily
	Third	Discontinue
Grade 3 cardiac arrhythmias	First	Withhold until recovery to \leq Grade 1 or baseline; may restart at 280 mg daily
	Second	Discontinue
Grade 3 or 4 cardiac failure Grade 4 cardiac arrhythmias	First	Discontinue
Grade 3 or 4 non-haematological toxicities Grade 3 or 4 neutropenia with infection or fever Grade 4 haematological toxicities	First	Withhold until recovery to \leq Grade 1 or baseline; may restart at original dose level

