7.6.1 Obinutuzumab Premedication

Obinutuzumab premedications should be reported to the investigator and recorded in the Case Report Form (CRF).

Prophylactic treatment against infection with co-trimoxazole and acyclovir is mandated for patients in receipt of ibrutinib and obinutuzumab combination therapy.

Patients with a high circulating lymphocyte count ($> 25 \times 10^9/L$) and/or renal impairment ($CrCl < 70$ mL/min) are considered at risk of TLS and should receive prophylaxis. They must receive treatment with uricostatics (e.g. allopurinol or adequate alternative) and hydration starting 12-24 hours prior to the infusion of obinutuzumab, as well as frequent monitoring of associated signs and symptoms. Corticosteroid premedication is mandatory for CLL patients in the first cycle. Premedication for subsequent infusions and other premedication should be administered as described below.

Please refer to Table 7 for premedications to reduce the risk of IRRs.

Table 7: Obinutuzumab premedications

Cycle Day of Treatment	Patients requiring premedication	Premedication	Administration
Cycle 1: Day 1	All patients	Intravenous corticosteroid ¹	Completed at least 1 hour prior to obinutuzumab infusion.
		Oral analgesic/anti-pyretic ²	At least 30 minutes before obinutuzumab infusion
		Anti-histaminic drug ³	
Cycle 1: Day 2	All patients	Intravenous corticosteroid ¹	Completed at least 1 hour prior to obinutuzumab infusion.
		Oral analgesic/anti-pyretic ²	At least 30 minutes before obinutuzumab infusion
		Anti-histaminic drug ³	
All subsequent infusions	Patients with no IRR during the previous infusion	Oral analgesic/anti-pyretic ²	At least 30 minutes before obinutuzumab infusion
	Patients with an IRR (Grade 1 or 2) with the previous infusion	Oral analgesic/anti-pyretic ²	At least 30 minutes before obinutuzumab infusion
		Anti-histaminic drug ³	
	Patients with a Grade 3 IRR with the previous infusion OR patients with lymphocyte counts $>25 \times 10^9/L$ prior to next treatment	Intravenous corticosteroid ¹	Completed at least 1 hour prior to obinutuzumab infusion.
		Oral analgesic/anti-pyretic ²	At least 30 minutes before obinutuzumab infusion
		Anti-histaminic drug ³	

¹ 100 mg prednisone/prednisolone or 20 mg dexamethasone or 80 mg methylprednisolone, hydrocortisone should not be used as it has not been effective in reducing rates of IRR.

² e.g. 1000 mg acetaminophen/paracetamol

³ e.g. 50 mg diphenhydramine

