7.11.2 For obinutuzumab: Discontinuation from Study Drug

Patients must discontinue study drug if they experience any of the following:

- Pregnancy
- PML

- Anaphylaxis, acute respiratory distress; prolonged or recurrent infusion reactions.
- Grade 4 IRR: Patient should be withdrawn immediately and treatment must be discontinued permanently
- Grade 3 IRR at re-challenge despite adequate premedication: Patient must be withdrawn immediately and treatment must be discontinued permanently
- Grade 3 or 4 neutropenia or thrombocytopenia as defined by the Modified IWCLL Response Criteria (revised 2008) (Appendix 2), that has not resolved to Grade ≤ 2 and requires a treatment delay to the next Cycle, Day 1 dose by 4 weeks
- Grade ≥ 2 non-haematological toxicity that does not resolve to Grade ≤ 1 /baseline and requires a treatment delay to the next Cycle, Day 1 dose by 4 weeks

Patients may also withdraw from all aspects of study participation including data collection.

Any patient who discontinues either study drug may continue ibrutinib or obinutuzumab monotherapy at the discretion of the clinician.

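### The mandatory obinutuzumab stopping list in 7.11.2 does not agree with 7.4.2 and 7.4.3 on neutrophil recovery or on repeated infusion reactions, and it cites an appendix that contains no toxicity grades

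*Protocol*

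**What the plan says.** **Neutrophils.** Protocol 7.4.3 opens its rule with "For participants who experience G3/4 neutropenia" and prints the range as <0.5-1.0 x10^9/L. The instruction is "we recommend treatment with G-CSF and to delay obinutuzumab until the neutrophils are back above" 0.5 x10^9/L. Section 7.4.1 prints 0.5 x10^9/L beside "Grade 4 neutropenia".

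Section 7.11.2 is introduced by "Patients must discontinue study drug if they experience any of the following". One of its triggers is "Grade 3 or 4 neutropenia or thrombocytopenia as defined by the Modified IWCLL Response Criteria (revised 2008) (Appendix 2), that has not resolved" to Grade 2 or better, joined by 'and' to a 4-week delay of the next Cycle, Day 1 dose.

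**Infusion reactions.** Another trigger in 7.11.2 reads "Anaphylaxis, acute respiratory distress; prolonged or recurrent infusion reactions". It carries no grade. Separate bullets in the same list cover a Grade 4 reaction and a Grade 3 reaction at re-challenge.

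Section 7.4.2 has its own list of reasons to give no further infusions: life-threatening acute respiratory symptoms, a Grade 4 reaction, or "a second occurrence of a Grade 3 (prolonged/recurrent) IRR (after resuming the first infusion or during a subsequent infusion". Table 5 slows and continues the infusion after a Grade 1-2 reaction and restarts it after a first Grade 3 reaction. Table 1 sets a starting rate for patients who reacted last time. Table 7 has a premedication row for "Patients with an IRR (Grade 1 or 2) with the previous infusion".

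**Grading.** Section 8.2.1.1 and Appendix 5 grade toxicity by CTCAE. Appendix 2 covers treatment-related lymphocytosis and disease progression.

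**The concern.** Both sets of rules decide whether a patient gets more obinutuzumab, and one of them is a permanent stop. Where they differ, two sites can treat identical patients differently and both be following the protocol. This matters statistically in two ways.

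- The extension measures whether adding obinutuzumab raises the MRD-negative rate, so exposure to obinutuzumab should be governed by one rule.
- The 12.6.2 guideline counts a related toxicity of Grade 3 or higher only if it ends therapy. Whether therapy ends may depend on which section the site followed.

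**Working it through.** The main check is a comparison of text, using only limits printed in the protocol.

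**1. Neutrophil grades.** 7.4.3 gives Grade 3/4 as <0.5-1.0, and 7.4.1 puts the Grade 4 boundary at 0.5. Counts between 0.5 and 1.0 x10^9/L are therefore Grade 3.

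**2. The delay in 7.4.3.** The release condition is a count above 0.5. A patient whose lowest count lies between 0.5 and 1.0 already meets it on the day of diagnosis. The section addresses Grade 3 and Grade 4 together, but its delay acts only on Grade 4.

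**3. The two neutrophil rules side by side.** The 7.11.2 trigger needs both parts: not resolved to Grade 2 or better, and a 4-week delay.

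| Situation | 7.4.3 | 7.11.2 | Conflict? |
|---|---|---|---|
| Count passes 0.5 before 4 weeks and the patient is re-dosed | Dose | Not triggered | No |
| Count below 0.5 at 4 weeks | Keep delaying | Discontinue | No; 7.11.2 caps the delay |
| Count above 0.5 and below 1.0 at 4 weeks | Dose | Discontinue | Yes |
| Count at Grade 2 or better at 4 weeks | Dose | Not triggered | No |

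Only the third row conflicts. An example is a patient held for a count below 0.5 who stands at 0.7 when the delay reaches 4 weeks.

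**4. The grading reference.** 7.11.2 points to Appendix 2 for Grade 3 or 4 neutropenia and thrombocytopenia. Appendix 2 grades neither, so the mandatory trigger rests on a definition that is not there.

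**5. Infusion reactions side by side.**

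| Event | 7.4.2, Tables 1, 5 and 7 | 7.11.2 |
|---|---|---|
| Second Grade 1-2 reaction | Continue, with adjusted rate and premedication | Stop, if the ungraded bullet is taken as written |
| First Grade 3 reaction | Restart after symptoms resolve | Stop, if the bullet is read as any prolonged Grade 3 reaction |
| Second Grade 3 reaction | Stop | Stop |
| Grade 4 reaction | Stop | Stop |

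**6. Link to 12.6.2.** The guideline accepts if at most 3 of 15 and at most 6 of 36 patients have a counted toxicity. With p the counted rate:

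P(accept) = Σ(x=0..3) C(15,x) p^x (1-p)^(15-x) × Σ(y=0..6-x) C(21,y) p^y (1-p)^(21-y)

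- p = 0.10: P(accept) = 0.905 (protocol: 90%).
- p = 0.30: P(detect) = 1 - 0.046 = 0.954 (protocol: 95%).

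The protocol's figures reproduce. To show sensitivity to the counted rate, assume other values of p: acceptance is 0.824 at 12%, 0.660 at 15% and 0.361 at 20%. These rates are assumptions. Nothing in the protocol says how far the inconsistency would move p.

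**The case against.** **The neutrophil rules can be read in sequence.** 7.4.3 says when to hold and release, and 7.11.2 says when a hold has lasted too long. This largely stands. A reader might infer that any patient at 0.7 is recovered in one section and unresolved in the other. The documents do not support that, because 7.11.2 also needs the 4-week delay and a patient released earlier never reaches it. The conflict at 4 weeks remains, as does the empty delay for Grade 3.

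**A recommendation gives way to a requirement.** 7.4.3 recommends and 7.11.2 commands, but the protocol states no order of precedence. Even if it did, the Grade 3 gap and the wrong appendix would remain.

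**The reaction bullet means Grade 3.** 7.4.2 attaches the words prolonged and recurrent to Grade 3, and the 7.11.2 bullet sits beside anaphylaxis. It is therefore fair to say that 7.11.2 does not expressly cover reactions of any grade; it gives no grade. However, 7.11.2 lists Grade 3 at re-challenge separately. If the bullet is limited to a second Grade 3 reaction, it duplicates that entry. If it covers a first Grade 3 reaction, it contradicts Table 5. If it covers lower grades, it contradicts Tables 1, 5 and 7. Only the redundant reading avoids a conflict, and a site cannot be expected to deduce that from a mandatory list.

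**The stopping guideline is advisory and ignores mild reactions.** Both statements are true. Section 12.6 says that the rules are not absolute, and stopping after a Grade 1-2 reaction can never be a counted event.

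**Conclusion.** The inconsistency is real, and narrower than it may first appear. Four things hold on the current text:

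- the 7.4.3 delay does nothing for a patient who is only Grade 3;
- 7.4.3 and 7.11.2 conflict for counts of 0.5-1.0 x10^9/L once the next Cycle, Day 1 dose has been delayed by 4 weeks;
- 7.11.2 cites an appendix without the grades it needs;
- the ungraded reaction trigger disagrees with 7.4.2 and Tables 1, 5 and 7 on every reading except a redundant one.

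The number of patients affected cannot be derived. A reader might apply the rates in section 1.4.1 to 40 patients: 34% with Grade 3-4 neutropenia gives 0.34 × 40 = 13.6, and 70.8% with an infusion reaction gives 0.708 × 40 = 28.3. Neither is a count of patients in conflict. The first includes everyone with Grade 3-4 neutropenia, whether or not it lasted 4 weeks. The second counts patients with any reaction, while the conflict mostly concerns repeats, and section 1.4.1 itself says that most patients had none from the second administration onward. Both rates also come from other regimens.

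The 12.6.2 count is exposed only through related Grade 3 or higher neutropenia, or Grade 3 reactions, that end therapy. This assumes that stopping obinutuzumab alone counts as cessation, which 12.6.2 does not say.

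Because these are permanent-stop rules, the text should be corrected even though the numbers may be small.

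**What to change.** Reconcile 7.4.2, 7.4.3 and 7.11.2:

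- State one neutrophil recovery criterion and use it in both 7.4.3 and 7.11.2.
- State whether the 7.4.3 delay applies to Grade 3 neutropenia or only to Grade 4.
- Replace the Appendix 2 reference in 7.11.2 with the CTCAE grading in Appendix 5.
- State one infusion-reaction stopping criterion, with its grade, and make 7.4.2, 7.11.2 and Tables 1, 5 and 7 agree with it.

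The thresholds and grades are for the clinical team to choose; this review takes no view on which of the present rules is right. The cost is an amendment to wording. Blood counts are already scheduled, so no new assessment is needed.

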7.5 IcCLLe Drug Supply, Labelling and Accountability

7.5.1 Drug Products (IMPs)

Ibrutinib

Ibrutinib is presented for oral administration as hard gelatine capsules containing 140 mg of Ibrutinib and will be supplied free of charge by Pharmacyclics.

Obinutuzumab

Obinutuzumab is provided as a single 1000 mg dose liquid concentrate with a strength of 25 mg/mL. It is supplied in 50 mL glass vials containing 40 mL of the 25 mg/mL liquid concentrate and will be supplied free of charge by F. Hoffman-La Roche Ltd for patients registered to the extension study. Refer to the appropriate IB and pharmacy manual for further details.

7.5.2 Labelling and Storage

Ibrutinib

Ibrutinib capsules are packaged in high-density polyethylene bottles with an induction seal and a child resistant screw-top cap. All packs will be provided fully labelled to comply with the relevant regulations.

Bottles containing capsules of ibrutinib should be stored at controlled room temperature of 15 -25 °C

Sufficient study drug will be provided for each study period at the beginning of the period. Multiple bottles may be dispensed at a single visit. Capsules should be dispensed in the original bottles provided. Further details can be found in the pharmacy manual.

Obinutuzumab

The recommended storage conditions for obinutuzumab drug product are between 2°C and 8°C and should be protected from light. For clinical formulation-specific and batch-specific instructions, and information on in-use stability, see the packaging label. Please refer to the pharmacy manual and SPC for further information on the storage and handling of obinutuzumab.

7.5.3 Treatment compliance and accountability

Ibrutinib should be retrieved from each patient at the end of each dispensing interval. The quantity of study drug and the date returned by the patient should be recorded on the patient specific drug accountability log. The details of the obinutuzumab prescribed and administered to each patient should also be recorded on the patient specific drug accountability log.

Depending upon the decision of the pharmaceutical company, remaining unused study drug supply will be returned to the supplier after the study is completed or will be discarded or destroyed at the clinical site. If the study drug is discarded or destroyed at the clinical site, standard institutional policy should be followed. Records documenting the date of study drug shipping or destruction, relevant lot numbers, and amount shipped or destroyed should be maintained.

In addition, all patients will be issued with a Patient Diary at each visit as necessary for the whole time they are on treatment. Patients will be asked to complete the diary, recording the time that each dose was taken, and whether any doses were missed. The diary also includes a section where the patient can record any relevant information such as side effects suffered or reasons for missed doses. The completed diary will be collected by the centre at clinic visits and returned to the IcCLLe Study Office.

Further details of supply, labelling and accountability can be found in the IcCLLe pharmacy manual.

7.6 Supportive Treatment

Ibrutinib Premedication **Prophylactic treatment against infection with co-trimoxazole and acyclovir is mandated for patients in receipt of ibrutinib therapy.**

No other specific premedications or supporting medications are required in conjunction with ibrutinib administration.

Supportive medications in accordance with standard practice (such as for emesis, diarrhoea, etc.) are permitted. The hematopoietic growth factors filgrastim and pegfilgrastim are allowed. Transfusions may be given in accordance with institutional policy.

Subjects with high tumour burden prior to treatment are considered to be at increased risk of tumour lysis syndrome:

Such subjects should be considered for hydration and treatment to prevent tumour lysis as per local practice prior to study treatment, as well as frequent monitoring of associated signs and symptoms.

7.6.1 Obinutuzumab Premedication

Obinutuzumab premedications should be reported to the investigator and recorded in the Case Report Form (CRF).

Prophylactic treatment against infection with co-trimoxazole and acyclovir is mandated for patients in receipt of ibrutinib and obinutuzumab combination therapy.

Patients with a high circulating lymphocyte count ($> 25 \times 10^9/L$) and/or renal impairment ($CrCl < 70$ mL/min) are considered at risk of TLS and should receive prophylaxis. They must receive treatment with uricostatics (e.g. allopurinol or adequate alternative) and hydration starting 12-24 hours prior to the infusion of obinutuzumab, as well as frequent monitoring of associated signs and symptoms. Corticosteroid premedication is mandatory for CLL patients in the first cycle. Premedication for subsequent infusions and other premedication should be administered as described below.

Please refer to Table 7 for premedications to reduce the risk of IRRs.

Table 7: Obinutuzumab premedications

Cycle Day of Treatment	Patients requiring premedication	Premedication	Administration
Cycle 1: Day 1	All patients	Intravenous corticosteroid ¹	Completed at least 1 hour prior to obinutuzumab infusion.
		Oral analgesic/anti-pyretic ²	At least 30 minutes before obinutuzumab infusion
		Anti-histaminic drug ³	
Cycle 1: Day 2	All patients	Intravenous corticosteroid ¹	Completed at least 1 hour prior to obinutuzumab infusion.
		Oral analgesic/anti-pyretic ²	At least 30 minutes before obinutuzumab infusion
		Anti-histaminic drug ³	
All subsequent infusions	Patients with no IRR during the previous infusion	Oral analgesic/anti-pyretic ²	At least 30 minutes before obinutuzumab infusion
	Patients with an IRR (Grade 1 or 2) with the previous infusion	Oral analgesic/anti-pyretic ²	At least 30 minutes before obinutuzumab infusion
		Anti-histaminic drug ³	
	Patients with a Grade 3 IRR with the previous infusion OR patients with lymphocyte counts $>25 \times 10^9/L$ prior to next treatment	Intravenous corticosteroid ¹	Completed at least 1 hour prior to obinutuzumab infusion.
		Oral analgesic/anti-pyretic ²	At least 30 minutes before obinutuzumab infusion
		Anti-histaminic drug ³	

¹ 100 mg prednisone/prednisolone or 20 mg dexamethasone or 80 mg methylprednisolone, hydrocortisone should not be used as it has not been effective in reducing rates of IRR.

² e.g. 1000 mg acetaminophen/paracetamol

³ e.g. 50 mg diphenhydramine

